1.6 Modifications from the approved statistical analysis plan

N/A. This is the first version of the SAP.

1.7 Determination of sample size

The planned minimum sample size is 402 patients. The primary endpoint for the study is technical performance, assessed as a binary outcome procedural success Yes/No. Procedural success will be assessed at the anastomosis level; each patient may have > 1 anastomosis. Based on data published in the medical literature (see RASM Literature Review Report [5]), the traditional failure and complication rate for vascular anastomoses is 15%, implying a success rate of 85%. The study will have 85% power to conclude that a success rate using Symani of 89% (or higher) is better than the literature value if a minimum of 402 anastomoses operations are performed. The percentage success will be estimated and exact 95% confidence limits calculated. If the lower 95% confidence limit exceeds 85% then the conclusion can be reached that Symani is superior to manual surgical methods. As each patient may have more than one anastomosis operation, the number of anastomoses will be ≥ 402 from 402 patients, providing increased power. As the number of anastomoses/patient is unknown at the time of study design, the conservative approach of recruiting 402 patients has been followed.

The number of patients missing a response for the primary endpoint will be monitored and additional patients may be recruited if deemed necessary.

There will be no predetermined limit to the number of sites that can participate in the study. Patients enrolled under the retrospective data collection protocol addendum will contribute to the planned sample size for the entire study (prospective plus retrospective).

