Target Population and sample size	The patients selected for this PMCF activity will be adults (over 18 years) requiring microsurgical reconstructive procedures applied to arterial, venous, neural or lymphatic anastomosis. The planned minimum sample size is 402 patients to ensure lower 95% confidence limit for the Primary Endpoint. A drop out rate of 5% will allow to include a total of 420 subjects. All subjects will be enrolled and followed in at least 3 EU centres until the sample size is reached.

**RASM
POST MARKET CLINICAL FOLLOW-UP
STUDY
Synopsis**

CDC-00031
Rev. 03
Page: 2/4

Duration of Study	Each enrolled subject will be followed through the first 30±7 days post-operatively or 24 weeks post-operatively (according to the procedures) per the follow-up schedule reflecting the standard of care.
Primary Endpoint	The primary endpoint will be defined as the ability to complete the surgical task with Symani as intended by the surgeon. This endpoint will be referred to as “Procedure Robotic Success”.
Secondary Endpoints	
The main secondary endpoint will be the rating of the surgeon experience of robot usability, which will be assessed using a questionnaire.
 
Further secondary endpoints will be assessed regarding the clinical outcome of the procedures. These criteria will differ depending on the procedure performed being a replantation, free flap surgery, lymphatic surgery or other.
 
Replantations
 
• Time for each anastomosis execution and warm ischemia time (minutes)• Intraoperative need to redo the anastomosis (yes or no)• Postoperative need to redo within 7 days (complication and need to return to the operating room to explore anastomosis: yes or no)• Complications• Replantation Failure or Loss (subsequent amputation) 
Free Flaps
 
• Time for each anastomosis execution and warm ischemia time (minutes)• Intraoperative need to redo the anastomosis (yes or no)• Postoperative need to redo within 7 days (complication and need to return to the operating room to explore anastomosis: yes or no)• Complications• Flap Failure or Loss (yes or no) 
Lymphatic Surgery
 
• Time for each anastomosis execution (in minutes)• Intraoperative need to redo based on ICG Patency (yes or no)• Postoperative need to redo based on ICG Patency (yes or no)• Complications• Limb volume reduction

**RASM
POST MARKET CLINICAL FOLLOW-UP
STUDY
Synopsis**

CDC-00031

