1. OVERVIEW AND INVESTIGATIONAL PLAN

1.1 Study design

The PRIMO study is a prospective, non-randomized, single arm, multicenter, post-market clinical follow-up (PMCF) study designed to evaluate the safety and effectiveness of the Symani System when used to assist microsurgical anastomoses in the real-world setting: i.e. it is a real world prospective observational data collection process. Patients selected will include adults (over 18 years) requiring microsurgical reconstructive procedures applied to arterial, venous, neural, or lymphatic anastomosis. Patients will be enrolled, undergo surgery, and have assessments made at regular intervals (day 1, day 4, day 14, day 30 (free flap), and 24 weeks (lymphatic anastomoses)).

An addendum to the PRIMO study was prepared and approved in December 2022. The addendum describes the addition of retrospective data collection to the PRIMO study. This will include patients with the same profile as the prospective data collected in the PRIMO study (i.e. ≥ 18 years requiring microsurgical reconstructive procedures applied to arterial, venous, neural, or lymphatic anastomosis) and will collect as much data as possible (based on availability) using the same data collection process as for the prospective data collection. Accordingly, the PRIMO study describes two data sources (prospective data collection and retrospective data collection), both collected under a common protocol. There will be some case report forms defined for prospective data collection (in the PRIMO protocol), specifically nurse and clinician questionnaires, which will not be available for the data collected retrospectively (in the PRIMO addendum).

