Replantations can be free flap or nerve.

In addition, recipient site has the same options as free flaps and will be collapsed into 4 categories as defined above for free flaps.

Anastomosis

Information is collected for each anastomosis, including type of vessel (artery, accompanying vein, superficial vein, nerve lymphatic, other), type of anastomosis (end-to-end, end-to-side, vein graft or flow through), vessel diameter, pedicle length and suture size. No derivations will be made unless some categories are sparsely populated in which case categories may be combined for data summaries.

The intended operation (manual or robotic) is recorded together with the number of robotic sutures used and the number of manual sutures used. The robotic and manual execution time is recorded.

Total procedure execution time will be derived where possible.

Sponsor: MMI Product: Symani system for microsurgical anastomosis Study: PRIMO	
Statistical Analysis Plan Final 22 November 2024	

No further derivations will be made.

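### The 85% success rule in SAP 1.7 rests on a vascular benchmark but is not limited to vascular anastomoses, and the SAP does not say which estimate it tests

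*SAP*

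**What the plan says.** **Benchmark and rule (SAP 1.7).** The planning figure is that "the traditional failure and complication rate for vascular anastomoses is 15%, implying a success rate of 85" per cent. The power statement reads "The study will have 85% power to conclude that a success rate using Symani of 89% (or higher) is better than the literature value", and it assumes at least 402 anastomoses of any kind. The method is "The percentage success will be estimated and exact 95% confidence limits calculated", and the rule is "If the lower 95% confidence limit exceeds 85% then the conclusion can be reached that Symani is superior to manual surgical methods". Neither the rule nor its conclusion names a vessel type or a surgery type.

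**Who is included.** The Protocol Synopsis (Target Population and sample size) covers "microsurgical reconstructive procedures applied to arterial, venous, neural or lymphatic anastomosis", and SAP 1.1 repeats this. SAP 2.1.2 allows a replantation to be of the nerve type. Under SAP 2.1.3.1, any anastomosis for which the surgeon intended the robotic approach counts towards the primary endpoint, whatever was being joined. No lymphatic or nerve benchmark appears anywhere.

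**What is recorded.** The anastomosis data are described as "including type of vessel (artery, accompanying vein, superficial vein, nerve lymphatic, other" (SAP 2.1.2).

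**How the primary endpoint is analysed.** SAP 2.4.4 and 2.4.4.1 tabulate and model free flaps, replantations and lymphatic surgery separately, and split replantations into free and nerve. Section 2.4.4.1 describes no estimate across surgery types, does not use vessel type as a stratum or model term, and does not mention 85%.

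**The concern.** A threshold taken from one kind of anastomosis is set against a set that contains other kinds. Nerve connections lie outside a vascular benchmark on any reading. For lymphatic connections the SAP does not say whether vascular is meant to include them.

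The number entering the rule is also undefined. Section 1.7 has one success percentage and one count of 402; section 2.4.4.1 has several estimates and no rule. If the rule is applied to everything together, the pooled rate is a weighted average whose weights are the case mix, and nothing in the plan fixes that mix. If it is applied type by type, the lymphatic and nerve results still have only a vascular figure to meet. At stake is the only prespecified superiority conclusion on the primary endpoint.

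**Working it through.** **Inputs from SAP 1.7:** benchmark 0.85, assumed Symani rate 0.89, n = 402, stated power 85%, exact 95% limits. Sidedness is not stated; two-sided is taken here. Anastomoses are treated as independent.

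**Step 1. The plan's own figure.** The cut-off is the smallest x whose Clopper-Pearson lower limit, BetaInv(0.025; x, 402 − x + 1), exceeds 0.85. At x = 355 the limit is 0.8476 and at x = 356 it is 0.8503, so the rule needs 356/402 = 88.6%.

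With X ~ Bin(402, p), P(X ≥ 356) is:
- p = 0.85: 2.4% (false-positive rate if every anastomosis is vascular)
- p = 0.89: 64.9%
- p = 0.90: 85.2%

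A one-sided 95% limit lowers the cut-off to 354 and gives 75.6% at 0.89. The stated 85% power is therefore not reproduced at 0.89.

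**Step 2. The rule applied to pooled data.** Let a share s of the 402 be non-vascular with success pN, and the rest vascular with success pV. The number of successes is the sum of two independent binomials, and the rule is met when that sum is at least 356. The expected pooled rate is (1 − s)·pV + s·pN. The documents give no value for s or pN, so these are assumptions shown over a range.

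| pV | pN | s | vascular / non-vascular n | expected pooled rate | rule met |
|---|---|---|---|---|---|
| 0.85 | – | 0% | 402 / 0 | 85.0% | 2.4% |
| 0.85 | 0.95 | 10% | 362 / 40 | 86.0% | 7.6% |
| 0.85 | 0.95 | 20% | 322 / 80 | 87.0% | 19% |
| 0.85 | 0.93 | 30% | 281 / 121 | 87.4% | 27% |
| 0.85 | 0.95 | 50% | 201 / 201 | 90.0% | 86% |
| 0.89 | 0.80 | 40% | 241 / 161 | 85.4% | 3.8% |

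In the first five rows vascular success only equals the benchmark, so each pass would be a wrong conclusion about vascular work. In the last row vascular success is at the planned 89% and is almost always missed; all 402 vascular at 89% would pass 64.9% of the time.

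**Step 3. Power if only vascular anastomoses are tested.** Same rule, true rate 0.89, with vascular cases as an assumed fraction of 402:

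| vascular share | n | cut-off | power |
|---|---|---|---|
| 50% | 201 | 181 | 37% |
| 60% | 241 | 216 | 43% |
| 70% | 281 | 251 | 48% |
| 80% | 322 | 287 | 51% |
| 90% | 362 | 322 | 55% |

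Power of 85% is first reached at about 639 vascular anastomoses, and stays at or above that level from about 676.

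**The case against.** The best defence is that the analysis section already separates surgery types. Section 1.7 never says that types are pooled, and 2.4.4.1 gives a rate with confidence limits for each type, with nerve replantations split off. A weak free-flap result would therefore be visible beside a strong lymphatic one. This stands, and it lessens the problem. It does not remove it: no rule is attached to those estimates, surgery type is not vessel type, and the conclusion in 1.7 remains unrestricted.

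A reader might go further and infer that nerve and lymphatic cases are the easy ones and would carry the claim while vascular performance is at or below benchmark. The documents do not support this. They give no success rate, difficulty or case mix for those connections, and the last row of the Step 2 table shows that mixing can equally hide a real advantage.

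It can also be said that vascular may have been meant to include lymphatic vessels. That is possible: the source is a literature report that the documents cite but do not reproduce, and SAP 2.1.3.2.3 matches lymphatic redo forms on vein diameter, so a vein is involved. Only the nerve mismatch is certain; the lymphatic one is an ambiguity to be settled.

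Finally, this is a single-arm post-market study whose stated objective is monitoring. That bears on severity, but 1.7 still licenses a superiority statement.

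**Conclusion.** The concern holds in this form: the 85% threshold describes vascular anastomoses, the rule built on it is not restricted to them, and sections 1.7 and 2.4.4.1 do not together say which estimate is tested. That much rests on the text alone.

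The size is conditional on pooling, independence, and the assumed rates and shares. With vascular success at exactly 85%, the chance of a wrong superiority conclusion rises from 2.4% to roughly 8–19% for a 10–20% non-vascular share at 95% success, and far higher for larger shares. In the opposite direction, a true vascular rate of 89% can be almost undetectable. The documents do not show which direction applies, nor that the rule will in fact be used on pooled data.

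This should be fixed. Because results are already to be shown by surgery type, it does not make the primary results uninterpretable.

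**What to change.** In SAP 1.7, apply the 85% comparison only to robotic-intended anastomoses in free-flap and replantation surgery whose recorded vessel type is artery, accompanying vein or superficial vein. Exclude lymphatic surgery by surgery type as well, so that a vein recorded in a lymphatic procedure does not enter. Report success for lymphatic, nerve and other connections with confidence limits but without the 85% test. Limit the conclusion to vascular anastomoses. In 2.4.4.1, name the single estimate to which the rule applies.

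No new data are needed, since vessel type is already on the anastomosis form; anastomoses with that field missing would need a stated handling rule, most likely among retrospective patients.

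The real cost is power, which the SAP should state: about 37–55% on a vascular subset of 50–90% of 402, against about 65% for all 402 and the 85% now claimed. Patients with several vascular anastomoses would raise the count, but those are not independent (SAP 2.4.4 acknowledges this), and the figures here ignore clustering. The change also gives up any benchmark claim for nerve and lymphatic work.

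It does not settle a separate matter: the benchmark counts failures and complications, while the endpoint in 2.1.3.1 turns on returns to conventional suturing for technical reasons.

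### SAP 1.7 claims 85% power at an 89% success rate, but 402 independent anastomoses judged by the planned exact 95% limit give about 65%; 85% is reached only at a true rate of about 90%

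*SAP*

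**What the plan says.** Section 1.7 of the SAP contains every input to the power claim.

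- **Comparator.** "the traditional failure and complication rate for vascular anastomoses is 15%, implying a success rate of 85" per cent.
- **Power and alternative.** "The study will have 85% power to conclude that a success rate using Symani of 89% (or higher) is better than the literature value".
- **Size on which that power rests.** The claim holds "if a minimum of 402 anastomoses operations are performed".
- **Method.** "The percentage success will be estimated and exact 95% confidence limits calculated".
- **Decision rule.** "If the lower 95% confidence limit exceeds 85% then the conclusion can be reached that Symani is superior to manual surgical methods".

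The same section plans 402 patients, notes that each may contribute more than one anastomosis, and treats any excess over 402 as extra power. It describes recruiting 402 patients as conservative because the number of anastomoses per patient was not known at design. It also allows further recruitment if primary responses are missing.

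The protocol synopsis gives the same minimum ("The planned minimum sample size is 402 patients to ensure lower 95% confidence limit for the Primary Endpoint") and adds: "A drop out rate of 5% will allow to include a total of 420 subjects".

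**The concern.** The power sentence is the only quantitative justification for the sample size, and it supports an explicit superiority conclusion. A gap of four percentage points between 85% and 89% is small for 402 binary observations, so 85% power looked too high for an exact two-sided 95% limit.

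If the figure is wrong, the plan's account of what the primary analysis can show is wrong too. On the stated basis of exactly 402 independent anastomoses, the chance of missing the claim at a true rate of 89% would be 35% rather than 15%. A sponsor who believes that 402 already secures 85% power also has less reason to use the recruitment flexibility in section 1.7.

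**Working it through.** **Inputs (all from SAP 1.7).** Null rate p0 = 0.85; alternative p1 = 0.89; n = 402 anastomoses; exact 95% limits, read first as two-sided (0.025 in the lower tail); success if the lower limit exceeds 0.85; stated power 85%. Independence of anastomoses is an assumption, needed for any exact binomial calculation.

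**Step 1: success threshold.** The exact (Clopper-Pearson) lower limit for x successes in n is the 0.025 quantile of a Beta(x, n − x + 1) distribution.
- x = 355: lower limit 0.8476, not above 0.85.
- x = 356: lower limit 0.8503, above 0.85.

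At least 356/402 = 88.6% is therefore needed. The type I error is P(X ≥ 356 | n = 402, p = 0.85) = 0.024.

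**Step 2: attempt to reproduce the stated 85%.** Power = P(X ≥ 356 | n = 402, p = 0.89) = **0.649**. The stated figure is not reproduced.

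**Step 3: other readings at the 95% level.** With a one-sided 95% limit (0.05 in the lower tail), 353 gives 0.8479 and 354 gives 0.8506. The threshold is 354, and power at 0.89 is **0.756**. Approximate methods at n = 402, p1 = 0.89:

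| Method | Two-sided 95% | One-sided 95% |
|---|---|---|
| Exact | 64.9% | 75.6% |
| Score | 62.8% | 75.4% |
| Wald | 72.7% | 82.1% |
| Null variance | 61.3% | 72.6% |
| Continuity-corrected score | 59.7% | 72.8% |
| Arcsine | 66.7% | 77.2% |
| Logit | 60.8% | 72.2% |

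None comes within two points of 85%. Using n = 420 instead gives 64.7% (exact, two-sided).

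**Step 4: which rate goes with 402 and 85%?** With the threshold still at 356, exact two-sided power by true rate is:

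| True rate | Power |
|---|---|
| 0.8900 | 64.9% |
| 0.8950 | 76.1% |
| 0.8975 | 81.0% |
| 0.9000 | 85.2% |

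The pair of 402 and 85% fits a true rate of about 90%.

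**Step 5: which size goes with 89% and 85%?** Exact power rises in a sawtooth as n grows. It first reaches 85% at n = 639 and stays at or above 85% from n = 676. The score formula gives 656. Spread over 402 patients, that is 639/402 = 1.59 to 676/402 = 1.68 independent anastomoses each.

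**Step 6: what several anastomoses per patient could do.** The documents give neither the mean per patient (m) nor the within-patient correlation (ρ), so the values below are assumptions that only show a range. Effective n = 402m / [1 + (m − 1)ρ], with exact two-sided power at 89% taken at the effective n rounded down.

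| m | ρ | Effective n | Power |
|---|---|---|---|
| 1 | – | 402 | 65% |
| 1.5 | 0.3 | 603/1.15 = 524 | 75% |
| 2 | 0.5 | 804/1.5 = 536 | 78% |
| 2 | 0.2 | 804/1.2 = 670 | 86% |
| 3 | 0.3 | 1206/1.6 = 754 | 89% |

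Clustering by surgeon, which SAP 2.4.4 expects, would lower the rows above m = 1 and could also lower the first.

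**Step 7: dropout (minor).** 420 × 0.95 = 399, three short of 402. 402/0.95 = 423.2, so 424 would be needed. 420 enrolled covers 1 − 402/420 = 4.3%.

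**The case against.** The strongest reply is that 402 is a floor. Section 1.7 expects at least that many anastomoses from 402 patients, and SAP section 2 describes several procedures, each with several anastomoses. With two or three per patient and modest correlation, power at 89% could reach 85% or more.

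This stands as a limit on the conclusion: a reader might infer that the study as a whole has 65% power, or a 35% chance of missing its claim at 89%, and the documents do not support that. It does not rescue the sentence, because section 1.7 attaches 85% to the minimum of 402 and counts extra anastomoses as a gain beyond it. SAP 2.4.4 itself says that repeated observations on a patient are not independent.

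Three other inferences should be resisted.

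- **That 89% must be a misprint for 90%.** The arithmetic fits, but the documents cannot show whether the rate or the power is the wrong number.
- **That power within each surgery type can be worked out.** SAP 2.4.4.1 models the primary endpoint separately by type, but no split between types is given and the 85% rule is not stated per type.
- **That 420 is an error of similar weight.** The gap is four enrolled patients. The primary endpoint is taken from the form completed for each anastomosis (SAP 2.1.3.1), so loss to later follow-up need not remove it. Further recruitment is also allowed.

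It is also fair to say that the error changes no endpoint, decision rule or analysis, and does not inflate the type I error.

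**Conclusion.** The concern holds for the power statement. On its own terms (402 anastomoses, 89% against 85%, exact two-sided 95% limit), the power is about 65%, some 20 points below the figure given. A one-sided 95% reading gives about 76%, still short. Both figures assume independent anastomoses. At 402, a power of 85% belongs to a true rate of about 90%.

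A 35% chance of missing the claim at 89% applies only if there are exactly 402 independent anastomoses. The power that the study will have is unknown, because it depends on the number of anastomoses per patient and on correlation within patients and surgeons. The dropout arithmetic is a side note.

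**What to change.** The sponsor should confirm whether the 89% or the 85% in section 1.7 is the slip, and restate the section with a matching pair. For example:

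*With 402 independent anastomoses and an exact two-sided 95% confidence interval, success requires at least 356/402; power is about 65% at a true rate of 89% and 85% at 90%.*

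The section should also say that:
- the calculation assumes independence, and correlation within patients and surgeons reduces the gain from several anastomoses per patient;
- the 85% rule applies to a named estimate. Section 1.7 refers to a single percentage with exact limits, while section 2.4.4.1 gives model-based results by surgery type, and nothing says which of them the rule governs.

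In the protocol synopsis, it is enough to state that 420 enrolled allows for about 4.3% dropout.

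The cost is wording in a SAP already marked final. No patients, endpoints or analyses need to change, though the stated power at 89% becomes less favourable.

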PRIMO	PRIMO Study Protocol	CDC-00031 Rev. 03 Page: 1/1
--------------	---------------------------------------	-----------------------------------

PRIMO Study Protocol

Protocol Number: CDC-00031

NCT04843436

SPONSOR DOCUMENT APPROVALS

Role	Name / Function
Issuer	[name] Clinical Operations Project Manager, Clinical Affairs
Reviewer & Approver	[name] Associate Director, Clinical Affairs
Reviewer & Approver	[name] VP, Regulatory Affairs

Reference ARENA PLM for document approvals and approval date.

Revision History		
REV	DATE	DESCRIPTION
00	10MAR2020	N/A, first issue
1.0	17NOV2020	Modified from Observational to Post-market clinical study
2.0	20OCT2021	Updates in accordance to EU MDR 2017/745 and ISO 14155:2020; Follow-up visit for free flap, replantation and other procedures extended to 30±7 days
3.0	11AUG2022	Addition of protocol description

**RASM
POST MARKET CLINICAL FOLLOW-UP
STUDY
Synopsis**

CDC-00031
Rev. 03
Page: 1/4

**PRIMO: Post-Market, Non-Randomized, Multicentre PMCF Study To Monitor
The Safety And Performance Of Symani System In Microsurgical
Reconstructive Procedures In A Real Life Setting**

Protocol Synopsis

Study Objectives	The objective of this PMCF study is to monitor the safety, usability, performance and long-term efficacy of the Symani System.
Study Device	Symani System for Microsurgery (Symani)
Indication for Use	
The Symani System is a CE-marked device and it is intended for soft tissue manipulation to perform microsurgery techniques such as anastomosis, suturing, and ligation on small anatomical structures, including blood vessels and lymphatic ducts, in open surgery procedures.
 
The Symani System teleoperated-instruments are indicated for use during microsurgical procedures when use of a motion scaling function is deemed appropriate by the surgeon.
 
The Symani System is not intended for use on the heart, central circulatory system, central nervous system, or the eye. The system is indicated for adult and pediatric use, even if in the present study, only adult population will be enrolled. It is intended to be used by trained physicians in an appropriate operating environment in accordance with the Instructions for Use.

Study Design	
A prospective, single-arm, open-label, clinical study designed to evaluate the Symani System safety and effectiveness for microsurgical anastomosis.
 
The study will be conducted in at least 3 centers in Europe.

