2.1.3.1 Primary effectiveness endpoint – Procedure Robotic Success

Form R or Anastomosis Data Form will be completed for each anastomosis. If the answer to the question 'How did you intend to perform this anastomosis' is 'Robotic' then the anastomosis is included for this endpoint.

The endpoint will be derived for each anastomosis using the question "Did you experience any system technical issues resulting in unplanned return to conventional suturing".

If the response is 'No' and the number of robotic sutures is > 0 or the number of robotic redo sutures is > 0, the anastomosis will be classified as 'intra-operative change from robotic to manual' = 'no'.

If the response is 'yes' anastomosis will be classified as intra-operative change from robotic to manual = 'yes'.

If there is no response to the question the anastomosis classification will be missing.

If the planned approach was manual the result will be N/A

The unit of analysis for this endpoint is the anastomosis.

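### The 85% rule in SAP section 1.7 cannot support superiority to manual surgery, because it sets a robotic-completion rate against a literature failure-and-complication rate

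*SAP*

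**What the plan says.** The decision rule is in SAP section 1.7: "If the lower 95% confidence limit exceeds 85% then the conclusion can be reached that Symani is superior to manual surgical methods". The threshold has a literature source, described in the same section as follows: "the traditional failure and complication rate for vascular anastomoses is 15%, implying a success rate of 85" per cent. The planning statement is "The study will have 85% power to conclude that a success rate using Symani of 89% (or higher) is better than the literature value", and it is tied to a count of at least 402 anastomoses.

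The rate to be compared with 85% is defined in SAP section 2.1.3.1. Only anastomoses intended as robotic count. The deciding item is "Did you experience any system technical issues resulting in unplanned return to conventional suturing". A negative answer, together with at least one robotic suture or robotic redo suture, is the favourable category. A positive answer is the unfavourable one. An anastomosis planned as manual is not applicable.

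The protocol synopsis describes the design as "A prospective, single-arm, open-label, clinical study". It admits arterial, venous, neural and lymphatic repairs, and SAP section 1.1 repeats this.

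**The concern.** The two rates measure different things. The reference counts how often a conventional vascular anastomosis fails or is followed by a complication. The endpoint counts how often the robot could be used without a technical breakdown. Manual surgery cannot have a robotic conversion, so it has no rate on this endpoint. Conversely, an anastomosis completed robotically may still be non-patent, be redone or be followed by a complication.

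What is at stake is the only stated decision rule for the primary endpoint. If it is applied as written, a statement about device reliability will be reported as clinical superiority over conventional surgery, and the result on the endpoint carries no information about whether that is true.

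**Working it through.** **Step 1. The two outcomes side by side.**

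| | Reference (SAP 1.7) | Endpoint (SAP 2.1.3.1) |
|---|---|---|
| Unfavourable event | failure or complication | technical issue forcing a return to conventional suturing |
| Defined for manual surgery | yes | no (not applicable) |
| Patency, redo, complications | failure and complication are what it counts | none enters |
| Tissue | vascular | arterial, venous, neural, lymphatic |

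The clinical outcomes are separate endpoints: intraoperative redo (2.1.3.2.3), postoperative redo (2.1.3.2.4), complications (2.1.3.2.5), flap or replantation loss (2.1.3.3.2) and patency (2.1.3.5.2). One anastomosis can score in opposite directions. Section 2.1.3.1 accepts robotic redo sutures as meeting the suture requirement, while section 2.1.3.5.2 scores a re-done anastomosis as not patent. No section links the two outcomes or argues that one can stand in for the other.

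**Step 2. Inputs for the rule.** Reference p0 = 0.85, planning value p1 = 0.89 and n = 402 anastomoses, all from SAP 1.7. Limits: "The percentage success will be estimated and exact 95% confidence limits calculated". Sidedness is not stated; I take two-sided 95%, that is, 2.5% in the lower tail. Anastomoses are treated as independent.

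**Step 3. Critical value.** The exact (Clopper-Pearson) lower limit for x successes is the 0.025 quantile of Beta(x, n − x + 1).

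- x = 355: lower limit 0.8476, rule not met.
- x = 356: lower limit 0.8503, rule met.

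The rule therefore needs at least 356/402 = 88.6%.

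**Step 4. The plan's own figure.** P(X ≥ 356) for X ~ Bin(402, 0.85) is 2.4%, and for Bin(402, 0.89) it is 64.9%. The stated 85% power is not reproduced. A one-sided 5% exact rule gives 75.6%. A true rate of 90% gives 85.2% with the two-sided limit. This is a separate matter, and the present point does not depend on it.

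**Step 5. Probability that the superiority statement is issued**, P(X ≥ 356) for X ~ Bin(402, p):

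| True completion p | Probability |
|---|---|
| 88% | 40.2% |
| 89% (SAP planning value) | 64.9% |
| 90% | 85.2% |
| 92% | 99.4% |
| 95% | >99.99% |

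All rows other than 89% are assumptions. The only argument is p, the completion rate; no clinical failure rate appears in the formula.

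**Step 6. The same rule on a clinical outcome.** Suppose, for illustration, that freedom from failure and complication were 80%, below the reference of 85%. Applied to that outcome, the rule would be met with probability P(X ≥ 356) for Bin(402, 0.80), which is below 0.1%. Applied to completion at an assumed 95%, it would be met almost always in the same patients. The answer depends on which outcome is put into the rule.

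**The case against.** The strongest reply concerns reach. The sentence stands only in the sample-size section. The primary analysis (SAP 2.4.4.1) and Appendix 1 estimate robotic success separately by surgery type, with no 85% threshold and no pooled test. The study objective is to monitor safety, usability, performance and efficacy. All of this is correct, and it limits the finding to one inferential sentence. It does not withdraw that sentence: it sits in a final SAP as the only rule for interpreting the primary endpoint.

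A second reply is that clinical failure would be visible. Redo, loss, patency and complications all have their own analyses. Three outcomes are also set beside external figures: flap survival 96.0% (2.4.4.3.1), re-operation 10.7% (2.4.6.2.4) and 30-day complications 31.6% (2.4.6.1). This stands too. A reader might infer that the plan hides poor clinical results or would let them pass unnoticed; the documents do not support that. They show only that those results have no bearing on the rule.

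Third, the tissue mismatch is partly handled, because tables and models are separated by surgery type, with nerve procedures split out within replantations. Only the pooled reading of section 1.7 is exposed.

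Fourth, the wider wording of the endpoint in SAP 1.3.1 (completing the task as the surgeon intended) might be thought closer to clinical success. It is still not freedom from failure and complication, and section 2.1.3.1 is the operative derivation.

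Finally, the source of the 15%, cited as [5], is not in the SAP reference list, so its exact make-up cannot be checked. That leaves open what the 15% contains in detail, but section 1.7 itself calls it a failure and complication rate.

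**Conclusion.** The point holds as one of definition. Exceeding 85% on Procedure Robotic Success shows that robotic completion exceeds 85%. It does not show superiority to manual surgery, whatever the data turn out to be.

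It is tempting to add that the superiority claim is virtually certain to be made. The documents do not support that. At the SAP's own 89% the probability is about 65%, and values above 99% require an assumed completion rate of about 92% or more. These probabilities also assume independent anastomoses, which SAP 2.4.4 says does not hold for repeat observations on a patient, and they rest on n = 402 and a two-sided reading of the limits. The conclusion about the wording needs none of these assumptions. It follows from sections 1.7 and 2.1.3.1 alone.

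**What to change.** In SAP section 1.7, delete the claim of superiority to manual methods. Replace it with wording such as: *If the lower 95% confidence limit is above 85%, the robotic completion rate exceeds the prespecified performance goal of 85%. This goal is not a completion rate for manual surgery.* No new data or patients are needed.

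Optionally, compare the 15% figure descriptively, labelled as a literature value, with a clinical outcome already collected in intended-robotic arterial and venous anastomoses. First-attempt patency is the simplest choice, because it is already derived per anastomosis. A redo or complication outcome at procedure level is an alternative. Two conditions apply:

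- The literature report must first be checked for how it defines the 15%, including its unit and time window. Until then no outcome can be called the matching one.
- Postoperative redo is derived per procedure and complications per patient. Including either needs a procedure-level unit or a rule for attributing events to anastomoses, and some retrospective data will be missing. This is more than one extra derived variable.

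The cost of the essential change is one amended sentence. The sponsor gives up a claim that the design cannot support.
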